### **5.1.3 Subject Exclusion Criteria**

The subject must be excluded from participating in the trial if the subject:

1. The subject is or has an immediate family member (e.g., spouse, parent/legal guardian, sibling or child) who is investigational site or sponsor staff directly involved with the trial.
2. The subject has fungal infection other than *Aspergillus* spp., Zygomycetes (including *Mucor* spp.) and *Fusarium* spp. infection.
3. The subject has allergic bronchopulmonary aspergillosis, allergic sinusitis of aspergillosis or aspergillosis of the eye.
4. The subject with long-term inactive aspergilloma which are not expected to develop the radiological response and clinical response by investigational product.
5. The subject is not expected to survive for this study duration.

6. The subject with an underlying disease, complication(e.g. bacterial pneumonia which is difficult to be distinguished from study target infection or aspiration pneumonia) or systemic condition which makes it difficult to evaluate the efficacy and safety of the study drug.
7. The subject has received any systemic antifungal therapy for the treatment of this infection who cannot discontinue this treatment or has improve/tend improve for this infection (The subject whose fungal infection does not improve/tend to improve can switch from existing medication to study drug).
8. The subject is expected to need prohibited medications in the following durations.

Table 13 Prohibited Medications

Prohibited Medications	Duration
Systemic antifungal therapy (oral, intravenous or inhaled) for treatment of this infection. Note that new antifungal therapy must not be started during the study medication for this infection.	Randomization to end of treatment
Investigational drugs (new chemical or biological entities): Investigational use of approved products or chemotherapy regimens may be permitted with the approval of the sponsor's project physician prior to use.	Prior 28 days of Day 1 to end of treatment
Prophylaxis of deep-seated fungal infection with systemic antifungal drugs.	Randomization to end of treatment
Medications that are known to interact with azole and may lead to life-threatening side effects (QT prolongation, ventricular arrhythmia including torsades de pointes etc.) : ebastine, pimozide and quinidine.	Prior 24 hours of Day 1 to end of treatment
Ergot alkaloids (ergotamine, dihydroergotamine or other licensed or investigational members of this class).	Prior 2 days of Day 1 to end of treatment
Medications that are known to result in a false positive galactomannan EIA (Aspergillus antigen) result: amoxicillin/clavulanate	From the date of informed consent to end of treatment
Medications known to lower the serum concentration/efficacy of azole antifungals: barbiturates a , carbamazepine, isoniazid, phenytoin, rifabutin, rifampicin b , and St John's Wort a (hypericum perforatum).	Prior 24 hours of Day 1 to end of treatment
Cyclophosphamide	Prior 24 hours of Day 1 to end of treatment
Ritonavir a and efavirenz	Prior 24 hours of Day 1 to end of treatment
Vinca Alkaloids	Prior 24 hours of Day 1 to end of treatment
Triazolam a	Prior 24 hours of Day 1 to end of treatment
HMG-CoA reductase inhibitors metabolized via CYP3A4 c	Prior 24 hours of Day 1 to end of treatment

a: After randomization, it is applicable to only the subject assigned to voriconazole treatment arm.

b: After randomization, it is applicable to the subject assigned to voriconazole treatment arm, but in case of co-administration in subject assigned to MK-5592 treatment arm, refer to the recommendation (Section 5.5.1).

c: After randomization, it is applicable to the subject assigned to MK-5592 treatment arm, but in case of co-administration in subject assigned to voriconazole treatment arm, refer to the recommendation (Section 5.5.1)

9. The subject meet the following criteria;
  - (1) The subject has received MK-5592.
  - (2) The subject has received voriconazole\* for this infection in the past, and has deep-seated fungal infection which is not effective for this treatment.
  - (3) The subject has intolerance for azole fungal treatment.
  - (4) The subject who is receiving two or more systemic antifungal combination therapy for chronic pulmonary aspergillosis at the time when informed consent is obtained.
10. The subject has known hypersensitivity including serious drug allergy, shock or anaphylaxis to any medication [including hypersensitivity to azole agents or rash (regardless of seriousness) caused by these agents].
11. The subject has any known history of Torsade de Pointes, a history of recent myocardial infarction within 90 days of study entry, or subject has a congenital or acquired long QT interval syndrome (including administration of drug which prolongs QT interval) or have a unstable cardiac arrhythmia.
12. The subject has QTc interval  $\geq$  450 msec on electrocardiogram performed at screening.
13. The subject has significant liver dysfunction (defined as total bilirubin  $>$  1.5 times upper limit of normal AND AST or ALT  $>$  3 times upper limit of normal on screening labs) at the time of randomization.
14. The subject has liver cirrhosis or cholestasis at the time of randomization.
15. The subject has renal insufficiency (estimated creatinine clearance  $<$  30 mL/min.) or on hemodialysis at the time of randomization or is likely to require dialysis during the study.  
In subject with estimated creatinine clearance of 30~50 mL/min and who receive IV formulation of MK-5592 or voriconazole, serum creatinine is carefully monitored. If serum creatinine is increased, switching to the oral therapy should be considered. Worsening of renal impairment may be occur due to accumulation of sulfobutylether-beta-cyclodextrine sodium.(creatinine clearance should be calculated by using Cockcroft-Gault Equation)
16. The subject has a known hereditary problem of galactose intolerance, Lapp lactase deficiency, or glucose-galactose malabsorption\*.
17. The subject has acute symptomatic pancreatitis within 6 months of study entry or has a diagnosis of chronic pancreatitis at the time of randomization\*.

18. The subject has an active skin lesion consistent with squamous cell carcinoma or melanoma at the time of randomization or a prior history of malignant melanoma within 5 year of study entry\*.
19. A subject has known or suspected Gilbert's disease at the time of randomization\*.
20. The female subject is pregnant, intends to become pregnant during 14 days from the end of study treatment, or is nursing at the time of randomization.
21. The subject has previously enrolled in this study.
22. The subject in the judgment of the investigator/sub investigator, is unfit for entry into this study.

\*: It is not applicable to the subject with zygomycosis or fusariosis.

## **5.2 Trial Treatments**

The treatments to be used in this trial are outlined below in [Table 14](#).

**Table 14 Trial Treatment**

Drug	Dose	Dose Frequency	Route of Administration	Regimen/Treatment Period	Use
MK-5592 (any one of oral tablet or IV solution must be selected)					
oral tablet	300 mg	QD (BID on Day 1)	Oral	84 days as a general rule	deep-seated fungal infection
IV solution	300 mg	QD (BID on Day 1)	Central intravenous		deep-seated fungal infection
Voriconazole (any one of oral tablet or IV formulation must be selected)					
oral tablet	200 mg (300 mg on Day 1)	BID	Oral	84 days as a general rule	deep-seated fungal infection
IV formulation	4 mg/kg(6 mg/kg on Day 1)	BID	intravenous		deep-seated fungal infection
If formulation is switched during the study, loading dose must not be administered again. From the date of switching formulation, maintenance dose administration should be continued.					

Trial treatment should begin on the day of randomization or as close as possible to the date on which treatment is allocated/assigned.

### **5.2.1 Dose Selection/Modification**

#### **5.2.1.1 Dose Selection**

Investigator / sub-investigator will select the initial formulation according to the subject's condition. Subjects who have central intravenous catheter or are judged to be able to administer via central venous at the timing of randomization by investigator will start with MK-5592 IV solution or voriconazole IV. Administration of MK-5592 IV solution or

voriconazole IV need to be considered for the subjects who present with or are expected to have intolerance to oral study drug administration (e.g. conditions which may interfere with oral intake or absorption of study drug such as vomiting or oral mucosal disorders). Subjects who are judged to be able to take the tablet at the timing of randomization by investigator will start with MK-5592 solid oral tablet or voriconazole tablet.

After the initiation of the IV formulation, transition from IV to oral therapy on or after Day 9 may occur when the subject is considered clinically stable and able to take oral administration by investigator's discretion. When switching the formulation, the investigator must evaluate the overall response. In case that subject who started using oral formulation cannot continue to receive the oral formulation during the treatment, investigator must evaluate the overall response at that time and conduct the discontinuation procedure. Data gathered on the day of switching formulation or preceding day can be used as an overall response at the switching formulation [However, if the subject is a patient with zygomycosis and joins the extension period, the switch of the formulation(iv↔tablet) could be done based on the subject's condition but dose modification of MK-5592 must not be allowed and the investigator does not need to evaluate the overall response at the timing of switching the formulation].

For subjects with estimated creatinine clearance of 30~50 mL/min who receive IV formulation of MK-5592 or voriconazole, serum creatinine is carefully monitored. If serum creatinine is increased, switching to the oral therapy should be considered. Worsening of renal impairment may occur due to accumulation of sulfobutylether-beta-cyclodextrine sodium.

#### 5.2.1.1.1 MK-5592 IV Solution

[Table 15](#) provides the dosing of MK-5592 for subjects randomized to the MK-5592 treatment arm if on IV therapy.

MK-5592 IV infusions will be prepared in 5% dextrose in water or saline. See the procedure separately for detail of MK-5592 IV formulation preparation. MK-5592 IV infusion is prepared as the time of use, but if necessary, the IV infusions may be prepared up to 18 hours prior to administration and stored at 2°C to 8°C refrigerated. The IV infusions should return to room temperature prior to administration.

MK-5592 IV will be given every 12 hours on Day 1, with infusions being not less than 9 hours or no more than 15 hours apart. The subsequent MK-5592 IV infusions will be administered once daily at approximately the same time every day with 24 hours apart, with infusions being not less than 21 hours or no more than 27 hours apart (infusions on Day 2 should not be less than 9 hours or no more than 15 hours apart). IV infusions should be administered for approximately 1.5 hours via a peripherally inserted central catheter or a dedicated lumen of a central venous catheter. Starting and stopping time of every infusion must be correctly recorded. Before and after infusion, investigator/sub-investigator will observe at the subject's infusion site.

If the dosing of study medication is delayed, the dose should be administered as soon as possible. Regarding the dose on or after Day 2, if it is more than 6 hours since the missed dose, the missed dose should be skipped and the next dose should be administered at the regularly scheduled time. Any missed doses should be properly documented in the subject's source documentation and eCRF.

Exceptionally, first dose could be in the night on Day 1. In case that the first dose is in the night, second dose could be in the morning on Day 2 approximately 12 hours apart from the first dose, third dose could be in the night on Day 2 approximately 12 hours apart from the second dose, and following doses from Day 3 could be in the night at approximately the same time every day with 24 hours apart with dosing being not less than 21 hours or no more than 27 hours apart. Also, if the dosing time need to be changed due to subject's schedule or operational handling (e.g., from QD dosing in pm to QD dosing in am), the dosing time could be adjusted within the range of allowance (scheduled time -/+3 hours). However, approximate dosing time needs to be fixed by Day 5(e.g. QD dosing is done at approximately 9:00am every day from Day 5).

Table 15 Dosing for MK-5592 IV Therapy for Cohort 2

	Day 1	Day 2-84*
Dose	300 mg BID	300 mg QD
Volume	250 mL (150 mL can be acceptable as needed)	
Infusion duration	1.5 hr	

\*: It should be conducted on or after Day 9 if subject need to switch the formulation of study drug.

### 5.2.1.1.2 MK-5592 Solid Oral Tablet

**Table 16** provides the dosing of MK-5592 for subjects randomized to the MK-5592 treatment arm if on oral therapy.

MK-5592 oral tablet will be given every 12 hours on Day 1, with being not less than 9 hours or no more than 15 hours apart, and will be given once daily at approximately the same time every day with 24 hours apart on or after Day 2, with doses being not less than 21 hours or no more than 27 hours apart (doses on Day 2 should not be less than 9 hours or no more than 15 hours apart). MK-5592 solid oral tablet can be administered with or without the food, investigator instructs that all cases should be properly documented in the administration diary (dosage amount, and food intake data within 2 hours before or within 1 hour after taking study drug etc.).

If the dosing of study medication is delayed, the dose should be taken as soon as possible. Regarding the dose on or after Day 2, if it is more than 12 hours since the missed dose, the missed dose should be skipped and the next dose should be administered at the regularly scheduled time. If a subject vomits within 15 minutes of MK-5592 solid oral administration, the dosing should be repeated as soon as possible, following appropriate antiemetic treatment. Any missed doses should be properly documented in the subject's source documentation and eCRF.

Exceptionally, first dose could be in the night on Day 1. In case that the first dose is in the night, second dose could be in the morning on Day 2 approximately 12 hours apart from the first dose, third dose could be in the night on Day 2 approximately 12 hours apart from the second dose, and following doses from Day 3 could be in the night at approximately the same time every day with 24 hours apart with dosing being not less than 21 hours or no more than 27 hours apart. Also, if the dosing time need to be changed due to subject's schedule or operational handling (e.g., from QD dosing in pm to QD dosing in am), the dosing time could be adjusted within the range of allowance (scheduled time -/+3 hours). However, approximate dosing time needs to be fixed by Day 5 (e.g. QD dosing is done at approximately 9:00am every day from Day 5).

Table 16 Dosing for MK-5592 Oral Therapy for Cohort 2

	Day 1	Day 2-84
Dose	300 mg(3 tablets) BID	300 mg(3 tablets) QD

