#### 5.2.1.1.4 Voriconazole Oral Tablet

Table 18 provides the dosing of voriconazole for subjects randomized to the Voriconazole treatment arm if on oral therapy.

Voriconazole tablets will be administered as a 300 mg dose BID on Day 1 (approximately 12 hour intervals with being not less than 9 hours or no more than 15 hours apart) and followed by 200 mg dose BID (at approximately the same time every day with approximately 12 hour intervals being not less than 9 hours or no more than 15 hours apart). Voriconazole oral tablets SHOULD NOT BE TAKEN WITH A MEAL, and all cases should be taken at least one hour before or one hour following a meal. Investigator should instruct subject that all doses should be properly documented in the administration diary (dosage amount, and food intake data within 1 hour before or within 1 hour after taking study drug etc.). If the dosing of study medication is delayed, the dose should be taken as soon as possible at least one hour before or one hour following a meal. If it is more than 6 hours since the missed dose, the missed dose should be skipped and the next dose should be administered at the regularly scheduled time.

If a subject vomits within 15 minutes of Voriconazole oral administration, the dosing should be repeated as soon as possible, following appropriate antiemetic treatment. Any missed doses should be properly documented in the subject's source documentation and eCRF.

Exceptionally, first dose could be in the night on Day 1. In case that the first dose is in the night, second dose could be in the morning on Day 2 approximately 12 hours apart from the first dose, third dose could be in the night on Day 2 approximately 12 hours apart from the second dose, and following BID doses from Day 3 could be in the morning and night at approximately the same time every day with 12 hours apart with dosing being not less than 9 hours or no more than 15 hours apart. Also, if the dosing time need to be changed due to subject's schedule or operational handling, the dosing time could be adjusted within the range of allowance (scheduled time -/+3 hours). However, approximate dosing time needs to be fixed by Day 5.

Table 18 Dosing for Voriconazole Oral Tablet

	Day 1	Day 2-84*
Dose	300 mg (6 tablets) BID	200 mg (4 tablets) BID

\* : Dose adjustment may be performed based on the trough concentration of voriconazole.

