### **7.2.1 Definition of an Overdose for This Protocol and Reporting of Overdose to the Sponsor**

In this trial, an overdose is any dose higher than the dose below for cohort 2.

MK-5592 solid oral tablet and IV solution: 300 mg/time and 300 mg/day (600 mg/day on Day 1).

Voriconazole IV: 6 mg/kg/time and 12 mg/kg/day on Day 1, 4 mg/kg/time and 8 mg/kg/day after Day 1

Voriconazole oral tablet: 300 mg/time and 600 mg/day on Day 1, 200 mg/time and 400 mg/day after Day 1

In case of higher than the above criteria, overdose is not applicable when the voriconazole dosage is adjusted based on the TDM, however overdose is any higher than 6 mg/kg for IV and 300 mg for oral tablet as a single dose.

In case of higher than the above criteria, overdose is not applicable when the MK-5592 and voriconazole daily dosage is exceeded according to the allowance of dosing interval by Day 5.

If an adverse event(s) is associated with (“results from”) the overdose of Sponsor's product or vaccine, the adverse event(s) is reported as a serious adverse event, even if no other seriousness criteria are met.

If a dose of Sponsor's product or vaccine meeting the protocol definition of overdose is taken without any associated clinical symptoms or abnormal laboratory results, the overdose is reported as a non-serious Event of Clinical Interest (ECI), using the terminology “accidental or intentional overdose without adverse effect.”

All reports of overdose with and without an adverse event must be reported within 24 hours to the Sponsor either by electronic media or paper. Sponsor Contact information can be found in the Investigator Trial File Binder.

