### **7.2.3 Immediate Reporting of Adverse Events to the Sponsor**

#### **7.2.3.1 Serious Adverse Events**

A serious adverse event is any adverse event occurring at any dose or during any use of Sponsor's product that:

- Results in death;
- Is life threatening;
- Results in persistent or significant disability/incapacity;
- Results in or prolongs an existing inpatient hospitalization;
- Is a congenital anomaly/birth defect;
- Is an other important medical event.

**Note:** In addition to the above criteria, adverse events meeting either of the below criteria, although not serious per ICH definition, are reportable to the Sponsor in the same timeframe as SAEs to meet certain local requirements. Therefore, these events are considered serious by the Sponsor for collection purposes.

- Is a cancer;
- Is associated with an overdose.

Refer to [Table 23](#) for additional details regarding each of the above criteria.

For the time period beginning when the consent form is signed until treatment allocation/randomization, any serious adverse event, or follow up to a serious adverse event, including death due to any cause, that occurs to any subject must be reported within 24 hours to the Sponsor if it causes the subject to be excluded from the trial, or is the result of a protocol-specified intervention, including but not limited to washout or discontinuation of usual therapy, diet, placebo treatment or a procedure.

For the time period beginning at treatment allocation/randomization through 14 days following cessation of treatment, any serious adverse event, or follow up to a serious adverse event, including death due to any cause, whether or not related to the Sponsor's product, must be reported within 24 hours to the Sponsor either by electronic media or paper. Electronic reporting procedures can be found in the EDC data entry guidelines. Paper reporting procedures can be found in the Investigator Trial File Binder (or equivalent).

Additionally, any serious adverse event, considered by an investigator who is a qualified physician to be related to the Sponsor's product that is brought to the attention of the

investigator at any time outside of the time period specified in the previous paragraph also must be reported immediately to the Sponsor.

All subjects with serious adverse events must be followed up for outcome.

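### Read literally, one tablet dose repeated after vomiting, as the protocol directs, exceeds the 7.2.1 daily overdose limit at the standard dose, and neither exemption covers it

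*Combined protocol and SAP*

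**What the plan says.** The tablet dosing sections direct a repeat after early vomiting in both arms. For MK-5592 (5.2.1.1.2): "If a subject vomits within 15 minutes of MK-5592 solid oral administration, the dosing should be repeated as soon as possible". For voriconazole (5.2.1.1.4): "If a subject vomits within 15 minutes of Voriconazole oral administration, the dosing should be repeated as soon as possible".

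Section 7.2.1 defines overdose as any dose above listed limits. For MK-5592 these are "300 mg/time and 300 mg/day (600 mg/day on Day 1"; for the comparator tablet, "Voriconazole oral tablet: 300 mg/time and 600 mg/day on Day 1, 200 mg/time and 400 mg/day after Day 1".

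Two exemptions follow. The first concerns therapeutic drug monitoring (TDM): "overdose is not applicable when the voriconazole dosage is adjusted based on the TDM", with a ceiling of 300 mg for a single tablet dose. The second concerns dosing times: "overdose is not applicable when the MK-5592 and voriconazole daily dosage is exceeded according to the allowance of dosing interval by Day 5". A dose repeated after vomiting is not mentioned, and the section does not say whether a vomited dose counts towards the day's total.

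Every overdose must be reported to the Sponsor within 24 hours. Without symptoms or abnormal laboratory results it is a non-serious Event of Clinical Interest (ECI). If an adverse event results from it, "the adverse event(s) is reported as a serious adverse event, even if no other seriousness criteria are met". Section 7.2.3.1 adds that overdose-associated events are not serious under the ICH definition, but "these events are considered serious by the Sponsor for collection purposes".

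**The concern.** Two rules meet without being reconciled. A site that follows the dosing section gives a dose that, on a literal reading of 7.2.1, must be reported as an overdose. The section already exempts two other kinds of permitted dosing that would trip the limits, which suggests this third kind was overlooked.

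Both arms are affected: section 7.2 counts an active comparator provided by the Sponsor as Sponsor's product, and section 9.1 lists voriconazole among the supplies the Sponsor provides.

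The primary objective (3.1) is to compare safety, and 8.2.5.2 gives serious AE and serious drug-related AE between-group intervals as Tier 2 rows whatever their count. Vomiting is among the events planned for at about 10% to 20% (8.2.7), so the situation is foreseeable. Sites could also differ, some reporting every repeat and others none.

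**Working it through.** **Step 1: the limits against the schedule.** Inputs are the doses in Tables 16 and 18 and the limits in 7.2.1. Scheduled daily total = single dose × doses per day.

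| Regimen | Scheduled total (mg) | Daily limit (mg) | Total with one full repeat (mg) | Excess (mg) |
|---|---|---|---|---|
| MK-5592, Day 1 | 300 × 2 = 600 | 600 | 300 × 3 = 900 | 300 |
| MK-5592, Day 2 on | 300 × 1 = 300 | 300 | 300 × 2 = 600 | 300 |
| Voriconazole, Day 1 | 300 × 2 = 600 | 600 | 300 × 3 = 900 | 300 |
| Voriconazole, Day 2 on | 200 × 2 = 400 | 400 | 200 × 3 = 600 | 200 |

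The scheduled totals reproduce the limits exactly, so there is no headroom. The per-time limit is not exceeded; only the daily limit is.

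**Step 2: does a daily excess alone count?** Yes. The second exemption is needed only if exceeding the daily figure is itself an overdose.

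**Step 3: the exemptions.** The first applies to voriconazole adjusted on TDM, so never to MK-5592 and not to voriconazole at the standard dose. The second applies to shifts in dosing time that 5.2.1.1.2 and 5.2.1.1.4 allow until the time is fixed by Day 5. A repeat after vomiting is neither.

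**Step 4: cases outside the gap.**
- *Night start.* Only one dose falls on Day 1, so one repeat gives 300 × 2 = 600 mg, equal to the limit in both arms.
- *Voriconazole reduced on TDM.* At 100 mg BID, one repeat gives 100 × 3 = 300 mg, below 400 mg. Doses raised on TDM are exempt up to 300 mg per single dose.

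**Step 5: how many subjects.** Planned arms are 60 and 30, and the vomiting incidence of 10% to 20% comes from 8.2.7. The other three factors are not in the documents and are assumptions: 50% to 100% of subjects on tablets, 10% to 50% of those with vomiting having it within 15 minutes of a dose, and 10% to 30% of re-dosed subjects having a new adverse event attributed to the repeat.

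- Re-dosed, MK-5592: 60 × 0.5 × 0.10 × 0.10 = 0.3 to 60 × 1.0 × 0.20 × 0.50 = 6.
- Re-dosed, voriconazole: 30 × 0.5 × 0.10 × 0.10 = 0.15 to 30 × 1.0 × 0.20 × 0.50 = 3.
- Events made serious, MK-5592: 0.3 × 0.10 = 0.03 to 6 × 0.30 = 1.8 subjects.
- Events made serious, voriconazole: 0.15 × 0.10 = 0.015 to 3 × 0.30 = 0.9 subjects.
- At the midpoints (75%, 15%, 30%, 20%): 60 × 0.75 × 0.15 × 0.30 × 0.20 ≈ 0.4 and 30 × 0.75 × 0.15 × 0.30 × 0.20 ≈ 0.2 subjects.

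If one such subject were tabulated as serious, the row would move by 1/60 = 1.7 points (MK-5592) or 1/30 = 3.3 points (voriconazole), and not at all if that subject already had another serious event.

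**The case against.** **The repeat may replace a failed dose.** Nothing says a vomited dose is disregarded, but nothing says it counts either. Section 7.2.1 speaks of a dose that is taken, and in both dosing sections the vomiting instruction comes straight after the delayed-dose rules and just before the instruction to document missed doses. That placement supports reading the repeat as a substitute. This stands as an alternative reading, so what is shown is a conflict under the literal wording, not proof that every repeat is an overdose. It does not remove the need for clarification, since a site cannot tell which reading applies.

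**Serious-AE rows.** A reader might infer that the upgraded events enter the Tier 2 serious-AE rows and distort the safety comparison. The documents do not support that. Section 7.2.3.1 treats these events as serious for collection only, and 8.2.5.2 and Table 27 do not say whether collection-only events are tabulated.

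**Capturing these doses can be defended.** Absorption of the first dose is uncertain after vomiting, so exposure could reach twice the intended amount for MK-5592 after Day 1. An ECI record is cautious in a safety trial. This also stands, and it is the price of the exemption.

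**The reach is small.** The vomiting that prompts a repeat cannot result from it, so a new event attributed to the repeat is needed. Section 5.2.1.1 asks that IV treatment be considered for subjects expected not to tolerate oral dosing.

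**Conclusion.** The point holds as a minor drafting conflict in reporting. At the standard tablet dose, a repeat that the protocol directs exceeds the literal daily limit in both arms by 200 to 300 mg, except on a night-start Day 1, and neither exemption reaches it. The certain consequence of the literal reading is a 24-hour overdose report per repeat; the conditional one is that a non-serious event judged to result from the repeat is reported as serious.

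The arithmetic rests on two readings: that the vomited dose counts towards the day's total, and that the repeat is a full dose. The subject counts rest on the assumptions in the working; the likely effect is zero or one subject. A reader might infer a bias against one arm, but the rule applies alike to both tablets, the 8.2.5.2 intervals are descriptive, and no direction can be predicted. The documents give no serious-AE rate from which to illustrate a change in those intervals. Efficacy and sample size are not affected.

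**What to change.** Add to 7.2.1: *One repeat of the full scheduled tablet dose, given because the subject vomited within 15 minutes of dosing as directed in 5.2.1.1.2 or 5.2.1.1.4, is not an overdose; the repeat is recorded in the diary and eCRF, and any AE is assessed for seriousness on the other criteria.*

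The cost is one sentence, with no added subjects, visits or dosing changes. The small loss is the automatic ECI report where the first dose was partly absorbed; the repeat stays traceable through the diary and eCRF, and events meeting the ordinary criteria remain serious. If the sponsor wants to keep that report, a narrower alternative is to retain the ECI and drop only the automatic upgrade to serious.
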